8.4.4 Sample Processing and Storage

Following collection, the sample will be immediately gently mixed by inversion 8-10 times. The sample will be stored on wet ice until centrifugation.

- The sample will be centrifuged at 1500 x g for 15 minutes at 4° C within 60 minutes after the sample is drawn.
- The resultant plasma should be withdrawn in two aliquots:
 - 0.5 mL in Aliquot 1 (label as "PK Primary") and the remainder in Aliquot 2 (label as "PK Back-up") into two clearly labeled 2mL polypropylene screw cap cryovials.
- Secure the cryovial caps and within 60-120 min after collection, place the samples into storage at (-20°C to -70°C) until shipment.
- Backup samples (Aliquot 2) will be held at the study site at (-20°C to -70°C), until the end of the study or as requested by the sponsor.

8.4.5 Sample Labeling

Please label Aliquot 1 as “PK Primary” and Aliquot 2 as “PK Back-up”. Each tube must be labeled with the patient’s study registration number, the study I.D (APEC1621J), and the date and time the sample was drawn. Data should be recorded on the appropriate transmittal form found in RAVE.

8.5.1 Sampling Schedule

An initial sample was previously required at time of enrollment onto the APEC1621SC screening protocol. Two additional samples (optional) will be collected into Streck Cell-Free DNA BCT tubes at the timepoints:

(1) Cycle 5 Day 1

(2) At disease progression or end of protocol therapy (for patients receiving ≥ 5 cycles of therapy only)

Peripheral blood samples for circulating tumor DNA should be obtained as follows:

- For patients ≥ 10 kg collect 20 mLs (10 mL per tube x 2 tubes)
- For patients ≥ 5 kg but < 10 kg collect 10 mL (one tube)
- For patients < 5 kg research samples will not be collected

In all cases, blood draw volumes should strictly adhere to institutional limitations, taking other blood draws into consideration. However, if a reduction in volume is required, samples should be collected in 10 mL increments (ie. 0, 10, or 20 mL should be collected such that each Streck Cell-Free DNA BCT is completely filled).

Established institutional guidelines should be followed for blood collection via vascular access devices. Heparin should be avoided in pre-collection flush procedures. If therapeutic heparin dosing contamination is a possibility, venipuncture is recommended as a first choice collection method. If a Streck Cell-Free DNA BCT tube immediately follows a heparin tube in the draw order, we recommend collecting an EDTA tube as a waste tube prior to collection in the Streck Cell-Free DNA BCT.

For patients who do not have indwelling catheters, blood should be collected via

venipuncture. To guard against backflow, observe the following precautions:

- Keep patient's arm in the downward position during the collection procedure.
- Hold the tube with the stopper in the uppermost position so that the tube contents do not touch the stopper or the end of the needle during sample collection.
- Release tourniquet once blood starts to flow in the tube, or within 2 minutes of application.
- Fill tube completely.
- Remove tube from adapter and immediately mix by gentle inversion 8 to 10 times. Inadequate or delayed mixing may result in inaccurate test results.

8.5.2 Sample Processing

Samples do not need to be processed at the collection site.

8.5.3 Sample Labeling

Each tube must be labeled with the patient's study registration number, the study I.D (APEC1621J), and the date and time the sample was drawn. Data should be recorded on the appropriate transmittal form found in RAVE, which must accompany the sample(s).

8.5.4 Sample Shipping Instructions

Specimen should be shipped at room temperature to the BPC (address below). Upon arrival separation, extraction, and storage of plasma and cellular DNA will be performed. Samples should be shipped from Monday through Friday for Tuesday through Saturday delivery. If blood is collected in the Streck tube on Friday, over the weekend or on the day before a holiday, the sample should be stored in a refrigerator until shipped on the next business day. Ship by FedEx Priority Overnight using the COG FedEx account. Blood samples should be shipped the same day as collection, ship blood for Saturday delivery if shipped on Friday.

Ship specimens to the following address:

Biopathology Center
Nationwide Children's Hospital
Protocol APEC1621J-Peds MATCH*
[name]*
[name]
[contact]
[contact]
Email: [contact]

*Be sure to include the room number. Packages received without the room number may be returned to the sender. Packages must be labeled "Peds MATCH" in order to expedite processing at the BPC.

9.0 AGENT INFORMATION

[figure not shown]
9.1 **BVD-523FB (ulixertinib)**
NSC# 799018 IND# 134661

9.1.1 Structure and molecular weight

Chemical Name: (S)-4-(5-chloro-2-(isopropylamino)pyridin-4-yl)-N-(1-(3-chlorophenyl)-2-hydroxyethyl)-1*H*-pyrrole-2-carboxamide hydrochloride

Molecular Formula: C₂₁H₂₂C₁₂N₄O₂·HCl

Molecular Weight: 469.79 g/mol for HCl salt

9.1.2 Supplied by:

BVD-523FB (ulixertinib) is supplied by BioMed Valley and distributed by a Division of Cancer Treatment and Diagnosis the Pharmaceutical Management Branch (DCTD), NCI.

9.1.3 Formulation

BVD-523FB (ulixertinib) is supplied as mono-chloride salt in hard gelatin capsule. Each yellow size 0 capsule contains 150 mg of drug substance (FB or free base equivalent) and is packaged in a 30-count white HDPE bottle with induction seal and child-resistant polypropylene cap.

9.1.4 Storage

Store at 15°C to 25°C (59°F to 77°F).

If a storage temperature excursion is identified, promptly return BVD-523FB (ulixertinib) to controlled room temperature and quarantine the supplies. Provide a detailed report of the excursion (including documentation of temperature monitoring and duration of the excursion) to [contact] for determination of suitability.

9.1.5 Stability

Shelf life studies are ongoing. Dispense BVD-523FB (ulixertinib) in the original

manufacturer's container. Do not repackage capsules.

9.1.6 Administration

See treatment ([Section 5.0](#)) and Dose Modification ([Section 6.0](#)) sections of the protocol. Take by mouth on an empty stomach either 1 hour before a meal or 2 hours after a meal. Capsules should not be opened, crushed or chewed. If a patient misses or vomits a dose, an additional dose should not be taken. Patients should resume dosing at the next scheduled time.

9.1.7 Potential Drug Interactions

In vitro studies suggest that BVD-523FB (ulixertinib) is metabolized primarily by CYP450-mediated oxidation, involving CYP isozymes 3A4, 2D6 and 1A2. Concomitant use of strong inducers or inhibitors of CYP 1A2, 2D6 or 3A4 is prohibited during the study.

In vitro and *ex vivo* results indicate that BVD-523FB (ulixertinib) has minimal potential to inhibit CYP 1A2, 2C9, 2C19, 2D6, 2E1, and 3A4 isozymes. The potential for BVD-523FB (ulixertinib) to affect CYP450 as an inducer is considered low even though some increases in CYP450 activity were observed in human hepatocyte and animal liver microsome systems.

BVD-523FB (ulixertinib) is a highly cell permeable, putative P-glycoprotein (P-gp) transporter substrate, and is highly protein bound in multiple species, including humans at 99-100% protein binding. Use caution in patients who are also receiving strong P-gp inhibitors or highly protein-bound drugs with narrow therapeutic ranges.

9.1.8 Patient Care Implications:

Advise patients to minimize sun exposure, use broad-spectrum sunscreens, and wear sunglasses. Patients should be informed that relevant sun exposure may occur even through glass, such as while driving.

Advise study participants to use contraception while receiving study treatment and for 3 months after the last dose of BVD-523FB (ulixertinib).

Inhalation of powder or contact with skin and mucous membranes, especially those of the eyes, must be avoided. Should accidental exposure of the eye or skin occur, copious irrigation with water should be instituted immediately.

9.1.9 BVD-523FB (ulixertinib) Toxicities

The Comprehensive Adverse Event and Potential Risks list (CAEPR) provides a single list of reported and/or potential adverse events (AE) associated with an agent using a uniform presentation of events by body system. In addition to the comprehensive list, a subset, the Specific Protocol Exceptions to Expedited Reporting (SPEER), appears in a separate column and is identified with bold and italicized text. This subset of AEs (SPEER) is a list of events that are protocol specific exceptions to expedited reporting to NCI (except as noted below). Refer to the 'CTEP, NCI Guidelines: Adverse Event Reporting Requirements' http://ctep.ca/cancer.gov/protocolDevelopment/electronic_applications/docs/aeguidelines.pdf for

further clarification. *Frequency is provided based on 208 patients.* Below is the CAEPR for BVD-523FB (ulixertinib).

NOTE: Report AEs on the SPEER **ONLY IF** they exceed the grade noted in parentheses next to the AE in the SPEER. If this CAEPR is part of a combination protocol using multiple investigational agents and has an AE listed on different SPEERs, use the lower of the grades to determine if expedited reporting is required.

Version 2.1, October 31, 2018¹

Adverse Events with Possible Relationship to BVD-523FB (ulixertinib) (CTCAE 5.0 Term) [n= 208]			Specific Protocol Exceptions to Expedited Reporting (SPEER)
Likely (>20%)	Less Likely (<=20%)	Rare but Serious (<3%)	
BLOOD AND LYMPHATIC SYSTEM DISORDERS			
	Anemia		Anemia (Gr 2)
		Thrombotic thrombocytopenic purpura	
CARDIAC DISORDERS			
		Heart failure	
ENDOCRINE DISORDERS			
	Hypothyroidism		Hypothyroidism (Gr 2)
EYE DISORDERS			
	Blurred vision		Blurred vision (Gr 2)
	Eye disorders – Other ² (eye symptoms)		Eye disorders – Other² (eye symptoms) (Gr 2)
		Eye disorders - Other (retinal vein occlusion)	
	Photophobia		Photophobia (Gr 2)
		Retinal detachment	
	Vision decreased		Vision decreased (Gr 2)
GASTROINTESTINAL DISORDERS			
	Abdominal pain		Abdominal pain (Gr 2)
	Bloating		Bloating (Gr 2)
	Constipation		Constipation (Gr 2)
Diarrhea			Diarrhea (Gr 2)
	Dry mouth		Dry mouth (Gr 2)
	Dyspepsia		Dyspepsia (Gr 2)
	Gastritis		Gastritis (Gr 2)
	Gastroesophageal reflux disease		Gastroesophageal reflux disease (Gr 2)
		Gastrointestinal disorders - Other (gastrointestinal hemorrhage) ³	
	Mucositis oral		Mucositis oral (Gr 2)
Nausea			Nausea (Gr 2)
	Vomiting		Vomiting (Gr 2)
GENERAL DISORDERS AND ADMINISTRATION SITE CONDITIONS			
	Chills		Chills (Gr 2)

Adverse Events with Possible Relationship to BVD-523FB (ulixertinib) (CTCAE 5.0 Term) [n= 208]			Specific Protocol Exceptions to Expedited Reporting (SPEER)
Likely (>20%)	Less Likely (<=20%)	Rare but Serious (<3%)	
Fatigue	Edema limbs	Edema face	Edema limbs (Gr 2)
	Fever		Fatigue (Gr 2)
	Non-cardiac chest pain		Fever (Gr 2)
	Pain		Non-cardiac chest pain (Gr 2)
INFECTIONS AND INFESTATIONS			Pain (Gr 2)
	Infection ⁴		Infection⁴ (Gr 2)
INVESTIGATIONS			
	Alanine aminotransferase increased		Alanine aminotransferase increased (Gr 2)
	Alkaline phosphatase increased		Alkaline phosphatase increased (Gr 2)
	Aspartate aminotransferase increased		Aspartate aminotransferase increased (Gr 2)
	Blood bilirubin increased		Blood bilirubin increased (Gr 2)
	Creatinine increased		Creatinine increased (Gr 2)
		Electrocardiogram QT corrected interval prolonged	
	Lymphocyte count decreased		Lymphocyte count decreased (Gr 2)
	Neutrophil count decreased		Neutrophil count decreased (Gr 2)
METABOLISM AND NUTRITION DISORDERS			
	Anorexia		Anorexia (Gr 2)
	Dehydration		Dehydration (Gr 2)
	Hyperglycemia		Hyperglycemia (Gr 2)
	Hyperphosphatemia		Hyperphosphatemia (Gr 2)
	Hypoalbuminemia		Hypoalbuminemia (Gr 2)
	Hypocalcemia		Hypocalcemia (Gr 2)
	Hypokalemia		Hypokalemia (Gr 2)
	Hypomagnesemia		Hypomagnesemia (Gr 2)
	Hyponatremia		Hyponatremia (Gr 2)
MUSCULOSKELETAL AND CONNECTIVE TISSUE DISORDERS			
	Arthralgia		Arthralgia (Gr 2)
	Generalized muscle weakness		Generalized muscle weakness (Gr 2)
	Musculoskeletal and connective tissue disorder – Other (muscle twitch)		Musculoskeletal and connective tissue disorders – Other (muscle twitch) (Gr 2)
	Myalgia		Myalgia (Gr 2)
NEOPLASMS BENIGN, MALIGNANT AND UNSPECIFIED (INCL CYSTS AND POLYPS)			
		Neoplasms benign, malignant and unspecified (incl cysts and polyps) - Other (squamous cell carcinoma, keratoacanthoma-type, mid forehead)	
NERVOUS SYSTEM DISORDERS			
	Dizziness		Dizziness (Gr 2)
	Dysgeusia		Dysgeusia (Gr 2)

Adverse Events with Possible Relationship to BVD-523FB (ulixertinib) (CTCAE 5.0 Term) [n= 208]			Specific Protocol Exceptions to Expedited Reporting (SPEER)
Likely (>20%)	Less Likely (<=20%)	Rare but Serious (<3%)	
	Paresthesia		Paresthesia (Gr 2)
PSYCHIATRIC DISORDERS			
	Anxiety		Anxiety (Gr 2)
	Delirium		Delirium (Gr 2)
RENAL AND URINARY DISORDERS			
	Acute kidney injury		Acute kidney injury (Gr 2)
	Hematuria		Hematuria (Gr 2)
RESPIRATORY, THORACIC AND MEDIASTINAL DISORDERS			
	Cough		Cough (Gr 2)
	Dyspnea		Dyspnea (Gr 2)
	Sore throat		Sore throat (Gr 2)
SKIN AND SUBCUTANEOUS TISSUE DISORDERS			
	Alopecia		Alopecia (Gr 2)
	Dry skin		Dry skin (Gr 2)
		Erythema multiforme	
		Erythroderma	
	Nail changes		Nail changes (Gr 1)
		Palmar-plantar erythrodysesthesia syndrome	
	Photosensitivity		Photosensitivity (Gr 2)
	Pruritus		Pruritus (Gr 2)
Rash acneiform			Rash acneiform (Gr 2)
Rash maculo-papular			Rash maculo-papular (Gr 2)
	Skin and subcutaneous tissue disorders - Other (skin fissures)		Skin and subcutaneous tissue disorders - Other (skin fissures) (Gr 2)
	Urticaria		Urticaria (Gr 2)
VASCULAR DISORDERS			
	Hot flashes		Hot flashes (Gr 2)
	Hypotension		Hypotension (Gr 2)

¹This table will be updated as the toxicity profile of the agent is revised. Updates will be distributed to all Principal Investigators at the time of revision. The current version can be obtained by contacting [contact]. Your name, the name of the investigator, the protocol and the agent should be included in the e-mail.

² Eye symptoms may include floaters, night blindness, and watering eyes, and halo vision.

³ Gastrointestinal hemorrhage may include gastric hemorrhage, colonic hemorrhage, rectal hemorrhage, or other gastrointestinal tract hemorrhage.

⁴ Infection may include infections around the rectum, eyes, mucosa, and other sites.

Adverse events reported on BVD-523FB (ulixertinib) trials, but for which there is insufficient evidence to suggest that there was a reasonable possibility that BVD-523FB (ulixertinib) caused the adverse event:

BLOOD AND LYMPHATIC SYSTEM DISORDERS - Febrile neutropenia; Leukocytosis

CARDIAC DISORDERS - Atrial fibrillation; Myocardial infarction; Pericardial effusion; Sinus bradycardia; Sinus tachycardia

GASTROINTESTINAL DISORDERS - Anal pain; Colonic ulcer; Flatulence; Gastrointestinal disorders - Other (diverticulum); Hemorrhoids; Small intestinal obstruction; Stomach pain

GENERAL DISORDERS AND ADMINISTRATION SITE CONDITIONS - Gait disturbance

INVESTIGATIONS - Blood lactate dehydrogenase increased; Platelet count decreased; Weight loss; White blood cell decreased

METABOLISM AND NUTRITION DISORDERS - Hyperkalemia; Hypoglycemia

MUSCULOSKELETAL AND CONNECTIVE TISSUE DISORDERS - Arthritis; Back pain; Flank pain; Muscle cramp; Musculoskeletal and connective tissue disorder - Other (musculoskeletal stiffness)

NERVOUS SYSTEM DISORDERS - Headache; Ischemia cerebrovascular; Nervous system disorders - Other (neuropathy peripheral); Seizure

PSYCHIATRIC DISORDERS - Insomnia

RESPIRATORY, THORACIC AND MEDIASTINAL DISORDERS - Bronchopulmonary hemorrhage; Oropharyngeal pain; Pleural effusion; Pneumothorax; Stridor

SKIN AND SUBCUTANEOUS TISSUE DISORDERS - Hirsutism; Pain of skin; Scalp pain; Skin and subcutaneous tissue disorders - Other (skin lesion)

VASCULAR DISORDERS - Flushing; Hematoma; Thromboembolic event

Note: BVD-523 in combination with other agents could cause an exacerbation of any adverse event currently known to be caused by the other agent, or the combination may result in events never previously associated with either agent.

9.2 Agent Ordering and Agent Accountability

NCI-supplied agents may be requested by eligible participating investigators (or their authorized designee) at each participating institution. The CTEP-assigned protocol number must be used for ordering all CTEP-supplied investigational agents. The eligible participating investigators at each participating institution must be registered with CTEP, DCTD through an annual submission of FDA Form 1572 (Statement of Investigator), NCI Biosketch, Agent Shipment Form, and Financial Disclosure Form (FDF). If there are several participating investigators at one institution, CTEP-supplied investigational agents for the study should be ordered under the name of one lead participating investigator at that institution.

Note: No starter supplies will be provided. Drug orders of BVD-523FB (ulixertinib) should be placed with CTEP after enrollment and treatment assignment to APEC1621J with consideration for timing of processing and shipping to ensure receipt of drug supply prior to start of protocol therapy. If expedited shipment is required, sites should provide an express courier account through the Online Agent Order Processing (OAOP) application. Provide the patient ID number in the comment box when submitting an order request.

9.3 Clinical Drug Request and Investigator Brochure Availability

Submit agent requests through the PMB Online Agent Order Processing (OAOP) application. The current versions of the IBs for the agents will also be accessible to site investigators and research staff through the PMB Online Agent Order Processing (OAOP) application. Access to OAOP requires the establishment of a CTEP Identity and Access Management (IAM) account and the maintenance of an “active” account status, “current” password, and active person registration status. For questions about drug orders, transfers, returns, or accountability call or email PMB anytime. Refer to the PMB’s website for specific policies and guidelines related to agent management. Questions about IB access may be directed to the PMB IB coordinator via email.

9.4 Agent Inventory Records

The investigator, or a responsible party designated by the investigator, must maintain a careful record of the receipt, dispensing and final disposition of all agents received from the PMB using the appropriate NCI Investigational Agent (Drug) Accountability Record

(DARF) available on the CTEP forms page. Store and maintain separate NCI Investigational Agent Accountability Records for each agent, strength, formulation and ordering investigator on this protocol.

10.0 CRITERIA FOR REMOVAL FROM PROTOCOL THERAPY AND OFF STUDY CRITERIA

10.1 Criteria for Removal from Protocol Therapy

- a) Clinical (including physical examination or serum tumor markers) or radiographic evidence of progressive disease (See [Section 12](#)).
- b) Adverse Events requiring removal from protocol therapy (See [Section 6](#)).
- c) Refusal of protocol therapy by patient/parent/guardian
- d) Non-compliance that in the opinion of the investigator does not allow for ongoing participation.
- e) Completion of 26 cycles of therapy.
- f) Physician determines it is not in the patient's best interest.
- g) Repeated eligibility laboratory studies (CBC with differential, bilirubin, ALT (SGPT) or serum creatinine) are outside the parameters required for eligibility prior to the start of protocol therapy (See [Section 8.1](#)).
- h) Study is terminated by Sponsor.
- i) Pregnancy
- j) Patient did not receive protocol treatment after study enrollment

Patients who are removed from protocol therapy during cycle 1 should continue to have the required observations in [Section 8.1](#) until the originally planned end of the cycle or until all adverse events have resolved per [Section 13.4.4](#), whichever happens LATER. The only exception is with documentation of the patient's withdrawal of consent from the APEC1621SC screening protocol. Patients who are removed from protocol therapy in subsequent cycles should have the necessary observations to ensure adequate clinical care.

10.2

Follow-Up Data Submission and APEC1621SC Off Study Criteria

Patients who are off subprotocol therapy will continue to be followed on the APEC1621SC screening protocol. Follow-up data submission will occur until one of the APEC1621SC Off Study Criteria is met (See Section 10 of APEC1621SC for details). Ongoing adverse events, or adverse events that emerge after the patient is removed from protocol therapy, but within 30 days of the last dose of investigational agent, must be followed and reported via RAVE and CTEP-AERS (if applicable). Follow-up data will be required until off study criteria are met unless consent is withdrawn or the patient dies or is lost to follow-up.

11.0 STATISTICAL AND ETHICAL CONSIDERATIONS11.1 **Sample Size and Study Duration**

APEC1621J will require a minimum of 4 evaluable patients and a maximum of 49 patients, allowing for 15% inevaluable. Assuming an enrollment rate of 10-30 biomarker positive patients per year, the primary cohort of this subprotocol is expected to be completed within 0.8-2.4 years.

11.2 **Dosing Considerations**11.2.1 **Pediatric MATCH Sub-arm Dosing in the Absence of Pediatric Phase 1 Data**

Please see [Section 5.1](#) for a specific discussion of the dosing of BVD-523FB (ulixertinib) to be used in this study. As there is no prior pediatric Phase 1 data, study investigators have reviewed relevant data with the pharmaceutical partner to identify a drug specific dosing plan for testing in children with relapsed or refractory cancer, and trial participants will be closely monitored to ensure tolerability of the selected dose. Limited pharmacokinetic sampling may be done for patients enrolled on these arms.

11.2.2 **Determination of Recommended Phase 2 Dose (RP2D)/Tolerable Dose**

Because the adult RP2D of the agent is the adult MTD, the pediatric subprotocol will evaluate an initial cohort of patients at a dose level approximately 30% below the adult MTD and then complete the study using the adult RP2D, assuming that both dose levels are tolerated.. The DLT evaluation period for the purpose of dose escalation will be Cycle 1 of therapy. Note that adverse events that begin during Cycle 1 and specify a duration of time in order to be considered a DLT must be followed to resolution or until the definition of DLT has been met, regardless of the schedule end of Cycle 1 (e.g. grade 2 thrombocytopenia would be considered a DLT if it developed during Cycle 1 of therapy and caused, or would have caused, a delay of >14 days to begin Cycle 2). Patients enrolled during the determination of the recommended Phase 2 dose who are not evaluable for toxicity during Cycle 1 at a given dose level will be replaced.

The rolling six phase 1 trial design²⁸ will be used for the conduct of this study. Two to six patients can be concurrently enrolled onto a dose level, dependent upon (1) the number of patients enrolled at the current dose level, (2) the number of patients who have experienced DLT at the current dose level, and (3) the number of patients entered but with tolerability data pending at the current dose level. Accrual is suspended when a cohort of six has enrolled or when the study endpoints have been met.

Dose level assignment is based on the number of participants currently enrolled in the cohort, the number of DLTs observed, and the number of participants at risk for developing a DLT (i.e., participants enrolled but who are not yet assessable for toxicity). For example, when three participants are enrolled onto a dose cohort, if toxicity data is available for all three when the fourth participant entered and there are no DLTs, the dose is escalated and the fourth participant is enrolled to the subsequent dose level. If data is not yet available for one or more of the first three participants and no DLT has been observed, or if one DLT has been observed, the new participant is entered at the same dose level. Lastly, if two or more DLTs have been observed, the dose level is de-escalated. This process is repeated for participants five and six. In place of suspending accrual after every three participants, accrual is only suspended when a cohort of six is filled. When participants are inevaluable for toxicity, they are replaced with the next available participant if escalation or de-escalation rules have not been fulfilled at the time the next available participant is enrolled onto the study.

The following table provides the decision rules for enrolling a patient at (i) the current dose level (ii) at an escalated dose level, (iii) at a de-escalated dose level, or whether the study is suspended to accrual:

# Pts Enrolled	# Pts with DLT	# Pts without DLT	# Pts with Data Pending	Decision
2	0 or 1	0, 1 or 2	0, 1 or 2	Same dose level
2	2	0	0	De-escalate*
3	0	0, 1 or 2	1, 2 or 3	Same dose level
3	1	0, 1 or 2	0, 1 or 2	Same dose level
3	0	3	0	Escalate**
3	≥ 2	0 or 1	0 or 1	De-escalate*
4	0	0, 1, 2 or 3	1, 2, 3 or 4	Same dose level
4	1	0, 1, 2 or 3	0, 1, 2 or 3	Same dose level
4	0	4	0	Escalate**
4	≥ 2	0, 1 or 2	0, 1 or 2	De-escalate*
5	0	0, 1, 2, 3 or 4	1, 2, 3, 4 or 5	Same dose level
5	1	0, 1, 2, 3 or 4	0, 1, 2, 3 or 4	Same dose level
5	0	5	0	Escalate**
5	≥ 2	0, 1, 2 or 3	0, 1, 2 or 3	De-escalate*
6	0	0, 1, 2, 3, or 4	2, 3, 4, 5 or 6	Suspend
6	1	0, 1, 2, 3 or 4	0, 1, 2, 3 or 4	Suspend
6	0 or 1	5 or 6	0 or 1	Escalate**
6	≥ 2	0, 1, 2, 3 or 4	0, 1, 2, 3 or 4	De-escalate*

* If six patients already entered at next lower dose level, the MTD has been defined.

** If final dose level has been reached, the recommended dose has been reached.

If two or more of a cohort of up to six patients experience DLT at a given dose level, then dose escalation will be stopped.

In addition to determination of the RP2D, a descriptive summary of all toxicities will be reported.

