2.5 Overview of Proposed Pediatric Study

This is a phase 2 trial of BVD-523FB (ulixertinib) in children with recurrent or refractory solid tumors, CNS tumors, non-Hodgkin lymphomas and histiocytic disorders harboring specific activating mutations that result in pathologic activation of the MAPK pathway.

Because the pediatric dose of BVD-523FB (ulixertinib) has not been established, there will be a limited dose finding phase consisting of the first 12 evaluable patients enrolled on study. BVD-523FB (ulixertinib) will be administered for 28-day cycles twice daily per nomogram by mouth on an empty stomach. The first 6 evaluable patients will be enrolled at a dose of 260 mg/m²/dose BID (450 mg BID Max Dose), equivalent to 75% of the maximum tolerated dose (MTD) in adults. There will be a single dose escalation to 350 mg/m²/dose BID (100% of the adult MTD [600 mg BID Max Dose]) or de-escalation to 175 mg/m²/dose BID (50% of the adult MTD [300 mg BID Max Dose]) for the next six subjects. Following the first 12 evaluable patients, all subsequent patients will be enrolled at the highest dose level not exceeding the pediatric MTD. Patients enrolled in the dose escalation component will be included in the analysis of efficacy.

The primary aim of this trial will be to establish the objective response rate to BVD-523FB (ulixertinib). While there will not be multiple pre-determined mutation-based cohorts, responses will be analyzed retrospectively with respect to specific MAPK pathway activating mutations.

Key secondary objectives include further evaluation of the tolerability of BVD-523FB (ulixertinib) in pediatric patients. Toxicity will be assessed using CTCAE V5.0. Imaging for disease evaluation will occur every other cycle x 3, then every three cycles. Disease response will be assessed according to RECIST v1.1 for solid tumors and 2-dimensional measurement for CNS tumors.

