5.1.1 Determination of Recommended Phase 2 Dose (RP2D)/Tolerable Dose

Dose Level	BVD-523FB (ulixertinib)Dose (mg/m ²)
-1	175 mg/m ² /dose PO BID* (300 mg BID Max Dose)
1*	260 mg/m²/dose PO BID* (450 mg BID Max Dose)
2	350 mg/m ² /dose PO BID* (600 mg BID Max Dose)

*Refer to the dosing nomogram in [Appendix V](#) for more information.

The starting BVD-523FB (ulixertinib) dose will be 260 mg/m²/dose (Dose Level 1), which is approximately 25% below the adult MTD. Accrual will be temporarily suspended after enrollment to the first 6 toxicity-evaluable subjects to assess for toxicity as outlined in [Section 11](#).

If there are fewer than 2 DLTs in the first 6 toxicity-evaluable subjects enrolled at the starting dose, the dose will be escalated to Dose Level 2. If ≥ 2 of the first 6 toxicity-evaluable subjects enrolled at Dose Level 2 have DLTs, all subsequent subjects will be enrolled at the original starting dose. Otherwise, remaining subjects will continue to enroll at Dose Level 2.

If there are 2 or more DLTs during cycle 1 among the first 6 toxicity-evaluable subjects enrolled at Dose Level 1, the next cohort will enroll at Dose Level -1. If ≥ 2 of the first 6 toxicity-evaluable subjects enrolled at the reduced dose have

DLTs, the study will be closed for toxicity. Otherwise, remaining subjects will continue to enroll at Dose Level -1.

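### Sections 2.5 and 5.1.1 (decide on six patients per level) and Section 11.2.2 (rolling six, which can escalate after three) assign the same patient different doses, and no text says which governs

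*Combined protocol and SAP*

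**What the plan says.** Section 2.5 describes fixed cohorts: "there will be a limited dose finding phase consisting of the first 12 evaluable patients enrolled on study". Within that phase, "The first 6 evaluable patients will be enrolled at a dose of" 260 mg/m²/dose BID (Dose Level 1), and six more follow at one other level.

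Section 5.1.1 pauses accrual once six toxicity-evaluable subjects are enrolled and bases the move up to Dose Level 2 on those six: "If there are fewer than 2 DLTs in the first 6 toxicity-evaluable subjects enrolled at the starting dose, the dose will be escalated". If two or more of the first six at Dose Level 2 have DLTs, "all subsequent subjects will be enrolled at the original starting dose".

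Section 11.2.2 adopts the rolling six design. "Dose level assignment is based on the number of participants currently enrolled in the cohort, the number of DLTs observed", together with the number still at risk of a DLT. Its worked example reads "if toxicity data is available for all three when the fourth participant entered and there are no DLTs, the dose is escalated", with the fourth patient entered at the next level. The decision table has the same Escalate outcome for 3, 4 or 5 enrolled patients with no DLT and no data pending. One footnote, on de-escalation, reads "If six patients already entered at next lower dose level, the MTD has been defined"; the other, on escalation, reads "If final dose level has been reached, the recommended dose has been reached". A closing sentence ends escalation once two or more patients in a cohort have DLTs.

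The cross-references run in a circle. Section 5.1.1 points to Section 11 for the toxicity assessment, and Section 11.2.1 points back to Section 5.1 for dosing. Section 3.8 says OPEN assigns the level but does not name the rule it applies.

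**The concern.** The two rules cannot both be followed on a path with no DLTs and mature data. There are three consequences.

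1. **Dose Level 1.** With 0 DLTs in 3 complete patients, Section 11.2.2 puts patient 4 at Dose Level 2. Sections 2.5 and 5.1.1 keep patients 4 to 6 at Dose Level 1.
2. **Dose Level 2.** The same table rows, with the second footnote, declare the recommended dose reached at 0/3, 0/4 or 0/5. Section 5.1.1 still tests the first six and can send later patients back.
3. **Return from Dose Level 2.** After two or more DLTs there, both texts send the next patient to Dose Level 1, and Section 5.1.1 keeps all later patients there. The first footnote defines the MTD only if six have already entered the lower level. It is silent on fewer than six, a case that arises only through the early escalation that Section 5.1.1 does not allow.

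Section 2.4.1 states that the agent has not been studied in children before. Sites, those who program OPEN, auditors and the monitoring committee could each follow the text and still disagree on whether a child was dosed per protocol.

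**Working it through.** **The plan's own counts.** Sections 2.5 and 5.1.1 give 6 + 6 = 12 evaluable patients, as stated. Rolling six can clear two levels with 3 + 3 = 6 if there are no DLTs, and can stop at 2 + 2 = 4 if each level has two DLTs in two patients. The minimum of 4 in Section 11.1 fits the latter.

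**Where the rules part.** They differ in three table rows (3, 4 or 5 enrolled, no DLT, none pending). If one DLT has occurred or data are pending, both keep the same level. At six complete patients both escalate on 0 or 1 DLT and de-escalate on 2 or more.

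**Dose difference for a reassigned patient** (Appendix V, total mg/day):

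| BSA (m²) | Level 1 | Level 2 | Increase |
|---|---|---|---|
| 0.54–0.72 | 300 | 450 | 50% |
| 0.73–1.07 | 450 | 600 | 33% |
| 1.08–1.29 | 600 | 900 | 50% |
| 1.3–1.58 | 750 | 1050 | 40% |
| ≥1.59 | 900 | 1200 | 33% |

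**How often the rules diverge at Dose Level 1.** Accrual is 10 to 30 per year (Section 11.1). Assume Poisson arrivals, full evaluability and a fixed time W from enrollment to complete data:
- W = 28 days is Cycle 1.
- W = 35 adds the 7 days allowed before starting therapy (Section 3.6).
- W = 49 adds 14 days for events followed past Cycle 1 (Section 11.2.2), applied to every patient, which is an extreme case.

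Let q = exp(−rate × W / 365.25), the chance that the gap to the next arrival exceeds W. At 10 per year and 28 days, q = exp(−0.767) = 0.465.

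With no DLTs, P(escalate before six) = 1 − (1 − q)³. At q = 0.465 this is 1 − 0.535³ = 0.847. The mean number of patients 4 to 6 given a different level is 3q + 2q(1 − q) + q(1 − q)².

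| W (days) | P at 10 / 20 / 30 per year | Mean patients moved |
|---|---|---|
| 28 | 85 / 52 / 27% | 2.0 / 1.1 / 0.6 |
| 35 | 77 / 38 / 16% | 1.8 / 0.8 / 0.3 |
| 49 | 60 / 19 / 5% | 1.3 / 0.4 / 0.1 |

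If 15% are inevaluable and replaced, simulation gives 88 / 57–60 / 30–34% at 28 days.

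Allowing for DLTs at an assumed rate p, with s = 1 − p, P = q·s³ + q(1 − q)·s⁴ + q(1 − q)²·s⁵. At q = 0.465 and p = 0.20 this is 0.238 + 0.102 + 0.044 = 0.383.

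| DLT rate | 28 days, 10 / 20 / 30 per year | 35 days |
|---|---|---|
| 10% | 58 / 35 / 18% | 52 / 25 / 11% |
| 20% | 38 / 22 / 11% | 34 / 16 / 7% |
| 30% | 24 / 14 / 7% | 21 / 10 / 4% |

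A separate simulation with the 35-day window agrees with the last column.

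**Chance of clearing one level.** Six rule: P(X ≤ 1), X ~ Bin(6, p). Rolling six, with data complete before each entry: (1 − p)³ + 3p(1 − p)⁵.

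| p | Six rule | Rolling six |
|---|---|---|
| 20% | 65.5% | 70.9% |
| 30% | 42.0% | 49.4% |
| 40% | 23.3% | 30.9% |
| 50% | 10.9% | 17.2% |

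The largest gap at any p is 7.7 points, at p = 36%. It is zero when six enroll before data mature.

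**Dose Level 2 after 0/3.** The chance that patients 4 to 6 alone supply two or more DLTs, on which Section 5.1.1 acts, is P(X ≥ 2), X ~ Bin(3, p): 10.4%, 21.6% and 28.2% at p = 20%, 30% and 35%. Multiplying by (1 − p)³ for the 0/3 itself gives 5.3%, 7.4% and 7.7%.

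**Return with fewer than six at Dose Level 1.** With assumed DLT rates of 10/20/35% at Dose Levels −1/1/2, simulation (30,000 runs per cell, standard error at most 0.3 points) gives 25 / 15 / 8% of trials at 10 / 20 / 30 per year with W = 28, and 17 / 6 / 2% with W = 49.

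**Final selection of Dose Level 2:**

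| DLT rates at −1/1/2 | Six rule | Rolling six (all accrual rates and windows) |
|---|---|---|
| 10/20/35% | 20.9% | 21.0–24.8% |
| 10/20/30% | 27.5% | 27.3–31.9% |
| 5/10/20% | 58.0% | 58.4–61.5% |
| 15/30/40% | 9.8% | 10.1–12.7% |

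Refilling Dose Level 1 to six on return, a reading no section states, leaves these figures unchanged. It moves the split between Dose Level 1, Dose Level −1 and closure by at most 2.9 points.

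**The case against.** The text gives hints of precedence. Section 5.1.1 refers to Section 11, Section 11.2.2 adopts rolling six for the whole study, the minimum of 4 fits rolling six, and Section 2.5 is only an overview. These hints do not settle it. The reference in Section 5.1.1 concerns assessing toxicity after six patients, and the same section then states its own six-patient trigger. Section 11.2.1 points back to Section 5.1.

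Assignment is central through OPEN, the Study Chair or Vice Chair is to be told before each enrollment, and study leadership reviews data weekly. Sites would therefore not apply different rules. That is a fair limit on the practical harm, but the protocol does not say which rule OPEN carries.

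The 85/52/27% figures assume no DLTs; at a 20% DLT rate they more than halve. The 10.4/21.6/28.2% figures are conditional on 0/3. Both points are right, and the unconditional values are given above.

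The return case does not change where the next patient goes; it leaves open only when the MTD counts as defined. That stands, so it is a secondary gap. Both dose levels are planned, and rolling six reaches the higher one early only after at least three complete DLT-free patients. That is also true, but it does not remove the conflict over which level a given child receives.

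**Conclusion.** The concern holds. Sections 2.5 and 5.1.1 contradict Section 11.2.2 on when Dose Level 1 is left and when Dose Level 2 is accepted, and nothing resolves it. The conflict is conditional: it needs no DLTs and no pending data when patient 4, 5 or 6 arrives. That is common at the slow end of planned accrual and uncommon at the fast end. The frequencies rest on assumed DLT rates, Poisson arrivals and a fixed data-maturity window.

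The effect on the level finally selected is small (at most 31.9 − 27.5 = 4.4 points in the four scenarios), and the single-stage response design is untouched. The case for correction is that the written rule for which dose a child receives cannot be carried out consistently as it stands. This review takes no position on which rule is preferable.

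**What to change.** Reconcile Sections 2.5, 5.1.1 and 11.2.2 to one rule of the sponsor's choosing. The edit should cover:

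- the adoption of rolling six in Section 11.2.2, its worked example, and the Escalate rows for 3, 4 and 5 patients with no DLT;
- both table footnotes;
- the six-patient and twelve-patient wording in Sections 2.5 and 5.1.1;
- the return after two or more DLTs at Dose Level 2, including when fewer than six have entered the lower level.

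Then confirm that the OPEN assignment logic (Section 3.8) applies the rule kept, and check the minimum of 4 in Section 11.1 for consistency with the 12 in Section 2.5.

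The cost is protocol wording and a check of the OPEN logic. Reconciling adds no patients in itself; the dose-finding number depends on the rule retained.
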